## Protocol Summary

Title	Percutaneous coronary interventions in patients treated with oral anticoagulant therapy
Acronym	PERSEO
Background	Percutaneous coronary interventions with stent (PCI-S) in patients requiring chronic oral anticoagulant therapy are associated with an increased risk of bleeding and ischemic complications. Limited data are available on the management of these patients, especially when oral anticoagulation is carried out with non-vitamin K antagonist (NOAC) which only recently have been introduced in clinical practice.
Objective	To evaluate in a “real world” setting the management and outcome of the different antithrombotic strategies used in patients with an indication for oral anticoagulant therapy, especially focusing on NOAC
Study Design	Prospective, multicenter, observational, controlled study
Sample size	At least 1080 patients treated with PCI-s and requiring oral anticoagulant therapy
Study sites	Approximately 30 or more Interventional Cardiology Centers across Italy
Co-Primary end-point	In the study there are two co-primary end-points: 
 
1. Describe the current management of antithrombotic therapy after the introduction of NOAC in patients requiring oral anticoagulant therapy undergoing PCI-S.
 
2. A combined measure of efficacy and safety endpoints, the so-called Net Adverse Clinical Event (NACE) end-point including major bleeding events + major adverse cardiac and
 

	cerebral events (MACCE) at one year follow up in patients treated with NOAC (and various combinations of antiplatelet therapy) compared to the corresponding strategies of vitamin K antagonists.
Secondary end-points	a. The individual components of the primary endpoint b. Major bleedings according to the International Society on Thrombosis and Haemostasis (ISTH) classification
Inclusion criteria	All patients undergoing percutaneous coronary interventions with stent and an indication for chronic anticoagulant therapy.
Exclusion criteria	- Patients of age < 18 years old - Lack of written informed consent to participate in the study

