A previous meta-analysis including all randomized phase II and III studies of NOAC in acute coronary syndromes showed that the combination of low dose NOAC and dual antiplatelet therapy is associated with a significant reduction in cardiovascular events at the price, however, of an increased risk of bleeding (11). Unfortunately, these studies did not include patients requiring chronic anticoagulant therapy.

Data regarding the combination of NOAC and antiplatelet therapy after PCI-S in patients requiring chronic anticoagulant therapy are currently scarce. Only recently, the randomized PIONEER study (12) showed the safety of the use of Rivaroxaban over warfarin in this setting of patients. In particular, the use of Rivaroxaban 15 mg combined with a single antiplatelet agent (mostly clopidogrel) was associated with a lower rate of clinically significant bleeding compared to standard therapy with a vitamin K antagonist plus dual antiplatelet therapy for 1, 6, or 12 months. However, the sample size of this study was not large enough to test accurately the efficacy in term of ischemic events prevention. Moreover, real world data on the use of the NOAC in combination with antiplatelet therapy after PCI-s in patients requiring chronic anticoagulant therapy are currently lacking.

Few years ago, in a previous observational Italian Registry (13), we presented the real world treatment of patients who underwent PCI-S and concomitant oral anticoagulant therapy with vitamin K antagonists. The study enrolled more than 400 patients and showed that there were no significant difference in term of ischemic events with triple therapy (vitamin K antagonist and dual antiplatelet therapy) or dual therapy (vitamin K antagonist and single antiplatelet agent) but all major bleeding episodes except one were detected in

the group of patients treated with triple (warfarin, aspirin and clopidogrel) therapy. However, in this Registry data on the association of antiplatelet and NAOC therapy were lacking because at that time these drugs were not available yet.

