## **2. Study Objectives**

The primary objectives of the study are:

1. To describe the contemporary antithrombotic management during and post PCI-S in patients treated with oral anticoagulant therapy
2. To evaluate, in this context, the efficacy and safety of the different NAOC compared to warfarin regimens.

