#### **4.4 Procedure and treatment regimen**

According to the observational design of the study, anticoagulant therapy (vitamin antagonists or new oral anticoagulant drugs), other pharmacological therapy as well as procedural device utilized, before, during the procedure and at follow-up will be left to the physician decision.

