## **5. Endpoints**

### **5.1 Primary end-point**

In the study there are two co-primary end-points:

1. Describe the current management of antithrombotic therapy after the introduction of NOAC in patients requiring oral anticoagulant therapy undergoing PCI-S.
2. A combined measure of efficacy and safety endpoints, the so-called Net Adverse Clinical Event (NACE) end-point including major bleeding events + major

adverse cardiac and cerebral events (MACCE) at one year follow up comparing patients treated with warfarin or NOAC.

Major bleedings are defined according to the Bleeding Academic Research Consortium (BARC) (14) including BARC 2, 3 and 5 events.

Major adverse cardiac and cerebral events include target vessel revascularization, myocardial infarction, stent thrombosis, stroke or transient ischemic attack and death.

Stent thrombosis is defined according to the Academic Research Consortium (ARC) definition (15) including definite, probable and possible stent thrombosis.

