## **6. Sample size calculation**

The sample size was estimated on the basis of the primary end-point (the rate of NACE at 1 year follow up) according to a previous observational study performed in Italy (13) with a rate of NACE of 27% in the warfarin group and according to the results of the PIONEER trial that showed a 10% reduction of NACE with rivaroxaban (12).

Consequently assuming a 25% incidence of NACE in the warfarin group, in order to detect a difference of 7% with a power of 80% and an alpha error of 0.05 the number required was calculated to be at least 540 patients per group (totally 1080 patients).

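### Co-primary end-point 2 is like for like by antiplatelet strategy in the Summary but ignores antiplatelet regimen in Section 5.1, and the stated 80% power covers only the second version

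*Combined protocol and SAP*

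**What the plan says.** The end-point that sets the sample size is worded in two ways.

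- **Protocol Summary, co-primary end-point 2:** NACE at one year in patients "treated with NOAC (and various combinations of antiplatelet therapy) compared to the corresponding strategies of vitamin K antagonists". Each NOAC combination is set against its VKA counterpart.
- **Section 5.1:** the same composite "at one year follow up comparing patients treated with warfarin or NOAC". Antiplatelet regimen is not mentioned.

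Other sections do not decide between them.

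- **Section 2**, objective 2, is to evaluate "the efficacy and safety of the different NAOC compared to warfarin regimens", which fits either version.
- **Section 5.3** does not list antiplatelet regimen. Its item on anticoagulant strategies concerns interruption or bridging around the procedure.
- **Section 6** sizes one two-group comparison: 25% NACE on warfarin, a 7-point difference, alpha 0.05 and 80% power, from which "the number required was calculated to be at least 540 patients per group".

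No stratification, adjustment or analysis model is given for this end-point. Section 4.4 says that drug therapy "before, during the procedure and at follow-up will be left to the physician decision".

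**The concern.** The two wordings are different estimands. The Summary asks what the anticoagulant does at a given antiplatelet regimen. Section 5.1 asks how NOAC patients fare against warfarin patients with whatever else each group received.

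The distinction matters here because NACE counts bleeding. Section 1.1 reports of the earlier Italian registry that "all major bleeding episodes except one were detected in" the triple-therapy patients, and that "there were no significant difference in term of ischemic events with triple therapy" as against dual therapy. If triple therapy is used more with one anticoagulant than with the other, the Section 5.1 comparison mixes the two influences. The direction is not known in advance.

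Two further things are at stake. With both wordings in force, the primary comparison can be chosen after the data are seen. And the planned effect may not carry over to a like-for-like comparison. Section 6 leans on a randomised rivaroxaban trial that Section 1.1 describes as rivaroxaban plus one antiplatelet agent against a VKA plus two. Part of the 7 points may therefore reflect regimen.

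**Working it through.** **Inputs from Section 6:** warfarin rate 25%, NOAC rate 25% − 7 = 18%, 540 per group, alpha 0.05. Sidedness is not stated; two-sided reproduces the plan's number. **Assumed, because the documents give neither:** the share of each group on triple therapy (written VKA/NOAC, in percent) and the NACE gap between triple therapy and the other regimens.

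**1. The plan's own figure.** Two proportions, pooled variance, mean rate 0.215:

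n = [1.96·√(2·0.215·0.785) + 0.8416·√(0.25·0.75 + 0.18·0.82)]² / 0.07² = (1.1387 + 0.4872)² / 0.0049 = 539.5, so 540 per group. Power at 540 is 80.0%. The figure is right for one unstratified test.

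**2. Unstratified test, no drug effect.** Spurious difference = mix difference × NACE gap. With less triple therapy on NOAC:

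| Mix difference (points) | NACE gap (points) | Spurious difference (points) | Rejection rate |
|---|---|---|---|
| 10 | 5 | 0.5 | 5.4% |
| 20 | 5 | 1.0 | 6.7% |
| 20 | 10 | 2.0 | 12% |
| 30 | 10 | 3.0 | 21% |
| 40 | 10 | 4.0 | 35% |

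With more triple therapy on NOAC, 30 and 10 give 3.0 points against NOAC and 20% rejection. In simulation, a regimen-stratified (CMH) test stayed at about 5%, with regimen as the only confounder simulated.

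**3. Unstratified test, true 7-point benefit, more triple therapy on NOAC.**

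- 45/55, gap 5: appears as 7 − 0.10·5 = 6.5 points; power 74%, against 80% stratified.
- 40/70, gap 10: appears as 7 − 0.30·10 = 4.0 points; power 35%, against 75% stratified.

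**4. Single stratified test, true 7 points within every regimen.** A stratum with a NOAC and b VKA patients has weight ab/(a + b). The sum of the weights over 270, its value without strata, is the information kept.

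- Mix differences of 0 to 30 points, either direction, gaps of 0 to 10 points: power about 75% to 81%.
- 80/40, no gap: 216·432/648 + 324·108/432 = 144 + 81 = 225; 225/270 = 0.833; power 72.5%.
- 90/30, no gap: 162·486/648 + 378·54/432 = 121.5 + 47.25 = 168.75; 168.75/270 = 0.625; power 59.5%.

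**5. Single stratified test when 7 points is the unstratified difference.** Like-for-like effect = 7 − mix difference × gap, with less triple therapy on NOAC:

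| Triple share VKA/NOAC | Gap (points) | Like-for-like effect (points) | Stratified power |
|---|---|---|---|
| 55/45 | 5 | 7 − 0.5 = 6.5 | 74% |
| 70/40 | 5 | 7 − 1.5 = 5.5 | 56% |
| 70/40 | 10 | 7 − 3.0 = 4.0 | 34% |

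The unstratified test keeps 80% in these rows, but partly by detecting the regimen mix. At 70/50 with a gap of 5, the effect is 6.0 points, power is 65%, and 765 per group would be needed for 80%.

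**6. Separate tests per strategy, 25% against 18% within each.** A strategy holding 70% of each group (378) has 65% power; 50% (270), 51%; 30% (162), 33%.

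**The case against.** **The unstratified contrast is legitimate.** The stated aim is to describe real-world practice, and a comparison of NOAC with VKA as actually used answers a fair question. This stands: choosing the estimand is the sponsor's decision. It does not excuse leaving both in force.

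**Evidence for a regimen gap is thin.** Section 1.1 gives no denominators by regimen. If most registry patients were on triple therapy, most bleeds would fall there anyway. This stands too, and it is why the results are shown as a range that starts where confounding is negligible.

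**The problem would be visible.** Co-primary 1 describes regimen use, and the secondary end-points report the NACE components, so a bleeding-driven difference would show. True, but neither yields a like-for-like estimate.

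**Stratifying is not free.** A reader might infer that one stratified analysis resolves everything at little cost in power and with no extra patients. The documents do not support that. Section 4.4 sets no limit on imbalance, and the planning effect draws on a trial described as a contrast across regimens. Section 6 does not say which rivaroxaban regimen its 10% reduction refers to, so how much of the 7 points is due to regimen cannot be determined. Section 1.1 also expects antiplatelet therapy to change within the year, so a discharge stratum does not describe the whole of follow-up.

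**Conclusion.** The contradiction is real and should be fixed. Its consequence depends on figures that the documents do not give. Under the assumed ranges, the Section 5.1 comparison runs from essentially unaffected (5.4% rejection with no drug effect) to seriously misleading (35%).

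Two stronger readings are not supported. One is that the Section 5.1 comparison will favour NOAC: the bias can go either way, and no mix is stated. The other is that the sample size is miscalculated: 540 per group is correct for what Section 6 describes.

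What Section 6 does not support is 80% power for the Summary's version. A single stratified test comes close if the regimen mix is similar and the like-for-like effect is still 7 points. It falls to between 74% and 34% in the examples where part of the 7 points is due to regimen. Separate tests per strategy, which the Summary wording also allows, are not powered.

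**What to change.** - **One contrast.** Use the same wording in the Summary, Section 2 and Section 5.1. If the Section 5.1 contrast is kept, say that it does not separate the anticoagulant from the antiplatelet regimen.
- **To carry out the Summary wording,** pre-specify a single NOAC versus VKA estimate stratified by, or adjusted for, antiplatelet regimen at discharge (anticoagulant plus dual, plus single, or alone). Report the unstratified estimate alongside, and add regimen to Section 5.3.
- **Section 6.** State that 80% power applies only to the unstratified 7-point comparison. Show stratified power over a range of mixes, labelled as assumptions. Re-justify 7 points as a like-for-like effect or restate the power. State that separate per-strategy tests are not powered.
- **Limits.** State that stratifying by discharge regimen does not remove other confounding, such as indication for anticoagulation or urgency of the procedure (Section 4.1), and does not capture later switching.

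The cost is wording changes, one extra analysis on medication data already collected under Sections 4.5 and 4.6, and a less favourable stated power. Whether more patients are needed depends on re-justifying the 7 points.

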## 1. INTRODUCTION

### 1.1 Background

Approximately 5 to 8% of patients undergoing percutaneous coronary interventions requires chronic anticoagulant therapy due to atrial fibrillation or other clinical entities (1-2). These patients pose particular problems when undergo percutaneous coronary intervention with stent implantation (PCI-S), because of the different antithrombotic and oral anticoagulant (OAC) strategies required after the procedure when dual antiplatelet therapy is recommended. Indeed dual antiplatelet therapy with clopidogrel and aspirin is superior to oral anticoagulation in term of stent thrombosis reduction (3) but OAC is superior to antiplatelet therapy for ischemic stroke reduction in patients requiring chronic OAC therapy for atrial fibrillation (4). Consequently, this scenario requires careful consideration balancing bleeding, stroke and acute coronary syndrome risks (5).

Recent guidelines on atrial fibrillation (6) suggest combined OAC and antiplatelet therapy to be modulated during follow up to prevent both thromboembolism and recurrent coronary events and/or stent thrombosis. In particular, a short period (1 month) of triple therapy (OAC, aspirin, clopidogrel) is recommended, followed by a period of dual therapy (OAC plus a single antiplatelet). However, in case of an acute coronary syndrome with stent implantation in atrial fibrillation patients at risk of stroke, a combination of triple therapy with aspirin, clopidogrel and an oral anticoagulant should be considered for 6 months to prevent recurrent coronary and cerebral ischemic events. For the first time these guidelines do not exclude the possible use of the new oral anticoagulants (NOAC) over warfarin and when NOAC are used, the consensus recommendation is that the lowest dose effective for stroke prevention in atrial fibrillation should be considered.

NOAC have been compared to warfarin for stroke prevention in the setting of atrial fibrillation and all these drugs showed a similar or improved efficacy over warfarin in term

of ischemic events as well as bleeding complications reduction (7-10). In particular, an important safety issue is the reduction of intracranial bleeding compared to warfarin. Currently, four different NOAC have been approved for the treatment of patients with atrial fibrillation: apixaban, edoxaban, rivaroxaban and dabigatran. The first three drugs are anti Xa inhibitors whereas the last one is a direct thrombin inhibitor.

A previous meta-analysis including all randomized phase II and III studies of NOAC in acute coronary syndromes showed that the combination of low dose NOAC and dual antiplatelet therapy is associated with a significant reduction in cardiovascular events at the price, however, of an increased risk of bleeding (11). Unfortunately, these studies did not include patients requiring chronic anticoagulant therapy.

Data regarding the combination of NOAC and antiplatelet therapy after PCI-S in patients requiring chronic anticoagulant therapy are currently scarce. Only recently, the randomized PIONEER study (12) showed the safety of the use of Rivaroxaban over warfarin in this setting of patients. In particular, the use of Rivaroxaban 15 mg combined with a single antiplatelet agent (mostly clopidogrel) was associated with a lower rate of clinically significant bleeding compared to standard therapy with a vitamin K antagonist plus dual antiplatelet therapy for 1, 6, or 12 months. However, the sample size of this study was not large enough to test accurately the efficacy in term of ischemic events prevention. Moreover, real world data on the use of the NOAC in combination with antiplatelet therapy after PCI-s in patients requiring chronic anticoagulant therapy are currently lacking.

Few years ago, in a previous observational Italian Registry (13), we presented the real world treatment of patients who underwent PCI-S and concomitant oral anticoagulant therapy with vitamin K antagonists. The study enrolled more than 400 patients and showed that there were no significant difference in term of ischemic events with triple therapy (vitamin K antagonist and dual antiplatelet therapy) or dual therapy (vitamin K antagonist and single antiplatelet agent) but all major bleeding episodes except one were detected in

the group of patients treated with triple (warfarin, aspirin and clopidogrel) therapy. However, in this Registry data on the association of antiplatelet and NAOC therapy were lacking because at that time these drugs were not available yet.

## **2. Study Objectives**

The primary objectives of the study are:

1. To describe the contemporary antithrombotic management during and post PCI-S in patients treated with oral anticoagulant therapy
2. To evaluate, in this context, the efficacy and safety of the different NAOC compared to warfarin regimens.

## **3. Study design**

Prospective, multicenter, observational, controlled study designed on patients requiring chronic anticoagulant treatment with either vitamin K antagonists or NOAC undergoing PCI-S for concomitant coronary disease.

## **4. Patient selection and follow up**

### **4.1 Inclusion criteria**

Patients with chronic disease requiring oral anticoagulant therapy (atrial fibrillation, prosthetic valves, previous pulmonary embolism, venous thrombosis) undergoing either elective, urgent or emergency percutaneous coronary interventions with stent implantation for acute or chronic coronary disease.

### **4.2 Exclusion criteria**

Patients are not eligible if any of the following applies:

- Patients of age < 18 years old
- Lack of written informed consent to participate in the study

#### **4.3 Informed Consent**

The Principal Investigator, Sub-investigator, or designee, who has been trained on the protocol, will explain the nature and scope of the study, potential risks and benefits of participation, and to answer questions of the subjects. All subjects or legally authorized subjects' representatives must sign the Ethics Committee (EC) approved informed consent prior to inclusion in the study. The signed informed consent will be kept in the subject's medical records and a copy will be given to the subject or the legally authorized representative.

#### **4.4 Procedure and treatment regimen**

According to the observational design of the study, anticoagulant therapy (vitamin antagonists or new oral anticoagulant drugs), other pharmacological therapy as well as procedural device utilized, before, during the procedure and at follow-up will be left to the physician decision.

#### **4.5 Follow up**

After the index event each subject will be followed with office follow-up visit at  $30 \pm 7$  days and  $12 \pm 1$  months. All follow-up visits are preferably scheduled as a visit to outpatient clinic. If patients are unable or unwilling to visit the outpatient clinic, the scheduled visit can be replaced by a telephone call.

Medication prescriptions are recorded at each follow-up visit. In case of an ischemic or bleeding event, the patient will be asked to provide documentation of the event as well as the troponin and hemoglobin values (when available).

#### **4.6 Data collection**

Patients are informed that data are collected at scheduled follow-up as well as at

unscheduled visits. The pre-procedural data to be collected include medical history, cardiac medications pre-PCI-S indication for PCI-S (elective, non-STEMI, or STEMI) and the reason for chronic anticoagulant therapy. The procedural details of the index PCI-S include location of treated lesions, number of stents, stent length, stent diameter, type of stents used and complications, the anticoagulant employed and its dose. The post-procedural medication is evaluated as well as clinical events (MACE and bleeding) that have occurred. INR is recorded if the patient is on chronic OAC with warfarin.

At each visit, the following information is collected:

- Medication prescription
- Major adverse cardiac and cerebral events
- Vital status
- Potential acute coronary syndrome
- Potential stroke of any etiology (ischemic, haemorrhagic and indeterminate)
- Stent thrombosis
- Any clinically overt bleeding events
- Coronary revascularization (PCI-S or coronary artery bypass grafting)

## **5. Endpoints**

### **5.1 Primary end-point**

In the study there are two co-primary end-points:

1. Describe the current management of antithrombotic therapy after the introduction of NOAC in patients requiring oral anticoagulant therapy undergoing PCI-S.
2. A combined measure of efficacy and safety endpoints, the so-called Net Adverse Clinical Event (NACE) end-point including major bleeding events + major

adverse cardiac and cerebral events (MACCE) at one year follow up comparing patients treated with warfarin or NOAC.

Major bleedings are defined according to the Bleeding Academic Research Consortium (BARC) (14) including BARC 2, 3 and 5 events.

Major adverse cardiac and cerebral events include target vessel revascularization, myocardial infarction, stent thrombosis, stroke or transient ischemic attack and death.

Stent thrombosis is defined according to the Academic Research Consortium (ARC) definition (15) including definite, probable and possible stent thrombosis.

